1.3 Schedule of Events

SoE Quick Link	Table Title
Table 1	Schedule of Events – Schedule A (Q3W Dosing)
Table 2	Schedule of Events – Schedule B (D1 & D8 Dosing)
Table 3	Schedule of Events – Schedule A (Q3W Dosing) if Step-Dosing is Implemented
Table 4	Schedule of Events – Schedule B (D1 & D8 Dosing) if Step-Dosing is Implemented

Table 1 Schedule of Events – Schedule A (Q3W Dosing)

Treatment Visit Window	SCR ^a	Treatment Period ^b (21-day cycles)									EOT ^c	RFU	LTFU ^e	Notes
		Cycle 1				Cycle 2				Cycle 3+				
		D1	D2	D4	D8	D1	D2	D4	D8	D1				
		0	0	0	±1	±3	0	0	±1	±3				
General and Safety Assessments														
Informed consent	X													
Eligibility criteria	X													
Demography	X													
Medical history	X													
Physical examination	X	(X)			X	X				X	X			Full physical exam at screening and end of treatment; brief physical exam at all other time points (ie, C1D8 and CXD1). (X): Not required if completed within 7 days of Day 1.
Height	X													
Weight	X	X			X	X				X	X			Dose adjustment required if weight changes $\geq 10\%$ from weight used for C1D1 dose (recorded at screening or C1D1 visit or per institutional standard).
Vital signs	X	X	X		X	X				X	X			All D1 assessments include a pre-dose (within 1 h prior to dose) and a post-dose assessment 1h after EOI (± 15 min). Measured in a semi-supine position after 5 min rest.
12-lead ECG	X	(X)			X						X			(X): Completed 6-24 hours after EOI
ECHO	X													If ECHO is not available or appropriate according to the institutional standard, then multi-gated acquisition (MUGA) scan is permitted
PFTs	X													
ECOG performance status	X	(X)			X					X	X			Must be confirmed per Section 8 before dosing C1D1 (X): Assessment can be performed within 48 hours prior to dosing
Hospitalization		X												24-hour hospitalization (may be extended per Investigator discretion). Patients should be advised to stay within a reasonable distance of the clinical site for the first week after the first dose.

	SCR ^a	Treatment Period ^b (21-day cycles)									EOT ^c	RFU	LTFU ^e	Notes	
		Cycle 1				Cycle 2				Cycle 3+					
		D1	D2	D4	D8	D1	D2	D4	D8	D1					
Treatment Visit Window		0	0	0	±1	±3	0	0	±1	±3					
AE review	(X)	←-----→												(X): Only collect AEs related to study-mandated procedures during screening period.	

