Weight	X	X			X			X			X	X	X	X			Dose adjustment required if weight changes ≥ 10% from weight used for C1D1 dose (recorded at screening or C1D1 visit or per institutional standard).
Vital signs	X	X	X		X			X			X	X	X	X			All D1 assessments include a pre-dose (within 1 h prior to dose) and a post-dose assessment 1 h after EOI (± 15 min). Measured in a semi-supine position after 5 min rest.
12-lead ECG	X	(X)						X						X			(X): Completed 6-24 hours after EOI
ECHO	X																If ECHO is not available or appropriate according to the institutional standard, then multi-gated acquisition (MUGA) scan is permitted
ECOG performance status	X	(X)						X				X		X			Must be confirmed per Section 8 before dosing on C1D1 (X): Assessment can be performed within 48 hours prior to dosing.
PFTs	X																
Hospitalization		X															24-hour hospitalization (may be extended per Investigator discretion). Patients should be advised to stay within a reasonable distance of the clinical site for the first week after the first dose.

	SCR ^a	Treatment Period ^b (21-day cycles)												EOT ^c	RFU	LTFU ^e	Notes	
		Cycle 1						Cycle 2				Cycle 3+						
		D1	D2	D4	D8	D9	D11	D1	D2	D4	D8	D1	D8					
Treatment Visit Window		0	0	0	±1	0	0	±3	0	0	±1	±3	±1					
AE review	(X)	←-----→															(X): Only collect AEs related to study-mandated procedures during the screening period.	
Concomitant medication review		←-----→															All AEs will be collected during the treatment period and followed for 30 days after the final dose of NL-201. All concomitant medications received within 28 days prior to the first dose of study treatment and up to 30 days after the last dose of study treatment will be recorded. In Parts 3 and 4, SAEs will be collected for 90 days following cessation of study treatment, or 30 days following cessation of study treatment if the participant initiates new anti-cancer therapy, whichever is earlier.	
Survival status																	X	
Parts 2 and 4: Subsequent anti-cancer therapy																	X	
Local Laboratory Assessments – all samples collected pre-dose unless otherwise indicated																		
Pregnancy test	X	(X)						X					X		X			WOCBP only. Must be confirmed per Section 8 before dosing on C1D1. Pregnancy tests may be performed more frequently as required by local regulations. (X): Sample can be collected within 48 hours prior to dosing.
Viral serology	X																	

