Cardiac toxicity	Minimal to mild myofiber degeneration and necrosis was noted in the highest dose of treated non-human primates in GLP toxicology experiments	
 • Early assessment: Patients will be required to have a recent baseline transthoracic echocardiogram and ECG prior to treatment with NL-201. • Testing: Clinical visits will include relevant safety parameters including blood pressure and pulse rate as well as questionnaire about symptoms including dizziness, syncope, and palpitations. Patients with clinical evidence of cardiovascular adverse events, including dizziness, hypotension, or syncope, will have a follow-up echocardiogram and ECG to identify potential compromise of cardiac function. • Clinical management: Depending on the severity of symptoms, patients with evidence of cardiac toxicity will be dose-reduced or receive no further doses of NL-201. Clinical support for acute cardiac toxicity can including IV fluid repletion, inotropic support, and antiarrhythmics.
Eosinophilia	GLP toxicology experiments showed minimal to moderate elevation of peripheral eosinophils, as well as increased interleukin-5 levels	
 • Patient selection: Patients with hypereosinophilic syndromes or eosinophils > 2 x the ULN will be excluded. • Frequent monitoring: Patient's peripheral eosinophil counts will be assessed regularly throughout the study. • Clinical management: Eosinophilia exceeding 1.5×10^3 per mm^3 can be managed with dose delays, with addition of IV steroids for patients with associated symptoms, such as rash, cough or diarrhea.
Capillary leak syndrome	Systemic high dose IL-2 therapy has been known to cause capillary leak syndrome, also called vascular leak syndrome, characterized by fluid retention,	
 • Early assessment: Patient weights, blood chemistry, and blood pressure will be assessed on D1 of each cycle during clinical visits, allowing early identification of patients retaining fluid. • Prevention: Patients may receive pre-medication per Section 6.1.3.

Potential Risk of Clinical Significance	Summary of Data/Rationale for Risk	Mitigation Strategy

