	peripheral edema, hypoalbuminemia, and hypotension.	
 Clinical management: Capillary leak syndrome should be managed per Investigator discretion and according to institutional guidelines, eg, peripheral edema can be managed by dose delay, diuretic, and/or compression stockings; hypotension can be managed with IV fluids, and if necessary, vasopressors.
Hepatotoxicity	Systemic high dose IL-2 can cause hepatotoxicity due to lymphocytic infiltration of the liver sinusoids.	
 Patient selection: Patients with comorbid viral hepatitis or elevation of transaminases > 3 x ULN are excluded from the study. Early assessment: Liver function is assessed during the study, allowing for identification of hepatic toxicities.
Splenic rupture	GLP toxicology experiments showed dose-dependent reversible enlargement of the spleen and lymph nodes due to leukocyte expansion.	
 Prevention: Patients will be advised to avoid high impact sports or other activities during the study
Potential risk of inflammation at the injection site	Inflammation was observed at the injection sites in the GLP toxicity studies	
 Patient monitoring: Patients are dosed in a hospital setting and monitored for evidence of inflammation at the injection site and/or extravasation of NL-201. Patients with injection site inflammation that is severe enough to require intervention can be dose-reduced or withdrawn from the study. Clinical management: In rats, inflammation of the injection site was mild to moderate and dose-dependent, while in monkeys, it was minimal to mild. In patients, mild injection site inflammation can be managed per local standard (eg, cold compresses, acetaminophen, diphenhydramine). Patients with more severe injection site inflammation can be treated with topical or systemic steroids, and/or dose reduced.
Renal toxicity	Renal tubular degeneration was observed at high doses in monkeys	
 Patient selection: Patients must have eGFR ≥ 50 mL/min/1.73 m², or creatinine WNL, to participate in the study. Early assessment: Renal function is assessed during the study, allowing for identification of renal toxicities.

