6.1 Study Drug(s) Administered

6.1.1 Investigational Products

Table 7 Investigational Products: NL-201 and Pembrolizumab

Intervention Name	NL-201	Pembrolizumab (Parts 3 and 4 only)
Type	Biologic	
Dose Formulation	Solution for infusion	Solution for infusion
Unit Dose Strength(s)		100 mg/vial
Dosage Level(s)	See Table 8 and Table 9	200 mg Q3W
Route of Administration	IV infusion	IV infusion
Dosing Instructions	NL-201 will be dosed as per the Pharmacy Instructions. IV dosing will occur either every 21 days (for Schedule A) or on Days 1 and 8 of every 21-day cycle (for Schedule B). For IV: patients that weigh ≥ 100 kg, the dose is capped as to not allow more than 100 times the current dose level to be administered to a patient at 1 time (see Table 8 and Table 9). Parts 3 and 4 only: NL-201 to be administered 30-60 minutes post administration of pembrolizumab.	Pembrolizumab will be administered using IV infusion on Day 1 of each 21-day cycle after all procedures and assessments have been completed. Pembrolizumab will be administered as a dose of 200 mg using a 30-minute IV infusion. Sites should make every effort to target infusion timing to be as close to 30 minutes as possible. However, given the variability of infusion pumps from site to site, a window between -5 minutes and +10 minutes is permitted (ie, infusion time is 30 minutes (-5 min/+10 min). After Cycle 1 trial treatment of pembrolizumab may be administered up to 3 days before or after the scheduled Day 1 of each cycle due to administrative reasons, however, pembrolizumab must always be administered on the same day as NL-201 when used in combination. The Pharmacy Manual contains specific instructions for the preparation of the pembrolizumab infusion and administration of infusion solution.
Hospitalization Guidance	Patients will remain in a hospital setting for the first 24 hours after completion of their first dose (IV) on study (may be extended per Investigator discretion), and for 8 hours after receiving subsequent doses. This period of hospital observation will be reduced to 2 hours for patients that have tolerated 3 consecutive doses. Required monitoring times may be adjusted by Neoleukin and/or per DMC recommendation pending review of safety data. Patients should also be advised to stay within a reasonable distance of the clinical site for the first week after the first dose.	
Use	Investigational	
Sourcing	Provided centrally by the Sponsor.	

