6.2.1.4 Step-Dosing

Pre-clinical studies of NL-201 suggest that symptomatic toxicity of NL-201 in animals peaks with the first dose, such that symptomatic toxicity caused by subsequent doses is attenuated compared to that caused by the first dose. Dose levels that are not tolerated when given as an initial dose become tolerated after giving 1 or more initial step-doses at a reduced (tolerated) dose level, and remain tolerated in subsequent doses. Thus, if a specific dose level is not well tolerated (ie, elicits DLTs in $\geq 33\%$ of patients), it is possible that tolerability can be improved by providing 1 or more reduced doses. Once the target dose is reached, subsequent doses would be given at the expected dose level for that cohort.

If step-dosing is implemented, dosing during the first cycle of step-dosing will be administered on Day 1 and Day 8 for both Schedule A and Schedule B patients, though in subsequent cycles Schedule A patients will resume Q3W dosing while Schedule B patients will continue Day 1+8 dosing.

The Cycle 1 dose used for step-dosing will be calculated as one half of the highest tolerated initial dose (HTID), ie, the highest initial dose at which $< 33\%$ of patients experience DLTs. Subsequent cycles will increase 1 dose level (DL) at a time to the CTD.

Table 10 Step-Dosing Guidance

Steps	Cycle 1				
	D1	D8	C2	C3	C4
1	0.5 x HTID	0.5 x HTID	CTD		
2	0.5 x HTID	0.5 x HTID	HTID + 1 DL	CTD	
3	0.5 x HTID	0.5 x HTID	HTID + 1 DL	HTID + 2 DL	CTD

C = cycle; CTD = cohort target dose; D = day; DL = dose level; HTID = highest tolerated initial dose

The DLT window for each patient during step-dosing will extend to include the cycle in which the patient first receives the CTD. The DLT window for each cohort is highlighted in gray in [Table 10](#).

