8 STUDY ASSESSMENTS AND PROCEDURES

- Only patients who meet all inclusion and exclusion criteria specified in [Section 5](#) will be enrolled in this study.
- Study procedures and their timing are summarized in the Schedule of Events ([Section 1.3](#)).
- Immediate safety concerns should be discussed with the Sponsor immediately upon occurrence or awareness to determine if the patient should continue or discontinue study drug.
- Adherence to the study design requirements, including those specified in the Schedule of Events, is essential and required for study conduct.
- All screening evaluations must be completed and reviewed to confirm that potential patients meet all eligibility criteria. The Investigator will maintain a screening log to record details of all patients screened and to confirm eligibility or record reasons for screening failure, as applicable. **ECOG and laboratory evaluations required for Cycle 1 Day 1 (within 48 hours prior to dosing) must conform to the following criteria prior to first dose of study drug on Cycle 1 Day 1:**
 1. Patients with ECOG performance status of 0 or 1
 2. Platelets $\geq 100,000/\text{mm}^3$
 3. ANC $> 1500/\text{mm}^3$
 4. Hemoglobin: Parts 1 and 2: ≥ 8.0 g/dL; Parts 3 and 4: ≥ 9.0 g/dL (NOTE: Criteria must be met without packed red blood cell transfusion within the prior 2 weeks. Participants can be on stable dose of erythropoietin [\geq approximately 3 months]).
 5. Lymphocyte count $\geq 500/\text{mm}^3$
 6. Eosinophils $< 1000/\text{mm}^3$

7. Renal function: eGFR \geq 50 mL/min/1.73 m² as determined by 2009 CKD-EPI equation,²⁹ or creatinine WNL
 8. AST and ALT: Parts 1 and 2: \leq 3x ULN, or \leq 5x ULN if known liver malignancy or metastasis; Parts 3 and 4: \leq 2.5x ULN, or \leq 5x ULN if known liver malignancy or metastasis
 9. TBL WNL, or \leq 3x ULN if known Gilbert's syndrome
 10. Coagulation: INR OR PT \leq 1.5 x ULN
 11. Highly sensitive pregnancy test (serum or urine) confirming no pregnancy
- Procedures conducted as part of the patient's routine clinical management (eg, blood count) and obtained before signing of the ICF may be utilized for screening or baseline purposes, provided the procedures met the protocol-specified criteria and were performed within the time frame defined in the Schedule of Events.

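### The weight note in Tables 1 to 4 makes an NL-201 dose adjustment mandatory at a 10% weight change with no exception for fluid retention, so edema can raise the µg dose by about 10%

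*Combined protocol and SAP*

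**What the plan says.** **The weight rule.** The Weight row in Tables 1, 2, 3 and 4 (Section 1.3) carries the same note: "Dose adjustment required if weight changes ≥ 10% from weight used for C1D1 dose". The reference weight may come from screening, the C1D1 visit or institutional practice. Section 8 makes the tables binding: "Adherence to the study design requirements, including those specified in the Schedule of Events, is essential and required for study conduct".

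**Dosing basis.** Tables 8 and 9 define dose levels in µg/kg. Table 7 (Section 6.1.1) adds that for patients of 100 kg or more "the dose is capped as to not allow more than 100 times the current dose level". It also states that "NL-201 will be dosed as per the Pharmacy Instructions"; that document is not part of the protocol.

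**Fluid retention.** Table 5 (Section 2.3.1) lists capillary leak syndrome as a potential risk. It has weight, chemistry and blood pressure checked on Day 1 of each cycle, "allowing early identification of patients retaining fluid". On management, it says that "peripheral edema can be managed by dose delay, diuretic, and/or compression stockings", at the investigator's discretion.

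**Toxicity rules.** In Table 11 (Section 6.2.2.1), capillary leak of Grade 3 or higher is held until Grade 2 or lower, and that row gives no level reduction. The edema/weight gain row reads no change, in the Grade 3 or higher column. The Grade 2 or lower cell is empty in both rows.

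**DLT window.** Section 6.2.1.4: "The DLT window for each patient during step-dosing will extend to include the cycle in which the patient first receives the CTD".

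**The concern.** The same measurement does two jobs that pull in opposite directions. Table 5 treats a rising weight as a warning of drug-induced fluid retention. The weight note treats it as a reason to recalculate a per-kg dose, and calls the adjustment required. A site that follows the note gives more drug to a patient who may be showing a toxicity of that drug.

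Three situations are open:
- capillary leak of Grade 2 or lower, for which Table 11 states no action;
- edema not diagnosed as capillary leak;
- a patient resuming after a hold for Grade 3 or higher capillary leak, now at Grade 2 or lower but still retaining fluid.

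Table 11 does not settle the matter. Its no-change entry may mean that the dose stays as it is, which conflicts with the note. It may equally mean that edema calls for no toxicity modification, which leaves the note in force. Neither place says which weight to use, so sites could act differently.

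Some of the affected doses could fall inside the DLT observation window of a first-in-human escalation.

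**Working it through.** **Inputs.** The trigger is a 10% change from the C1D1 dosing weight (Tables 1 to 4). The dose is level × weight, with the weight capped at 100 kg (Tables 7 to 9). The overdose threshold is 20%, taken as 20% above target (Section 8.5). A gain of 15% is an assumption for illustration; the note sets no upper limit. That the adjustment is proportional and upward is inferred from µg/kg dosing.

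**Check of the plan's own figures.** 100 kg × level gives the tabulated maximum for all 14 levels in Table 8, for example 3.0 × 100 = 300 µg and 12.0 × 100 = 1200 µg.

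**Size of the rise.** Relative rise = min(new weight, 100) / min(C1D1 weight, 100) − 1, applied when the gain is at least 10%.

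At 70 kg and 3 µg/kg:
- starting dose: 70 × 3 = 210 µg
- 10% gain (7.0 kg): 77 × 3 = 231 µg, +10%
- 15% gain (10.5 kg): 80.5 × 3 = 241.5 µg, +15%

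| C1D1 weight | Rise at 10% gain | Rise at 15% gain |
|---|---|---|
| 70 kg | 10% | 15% |
| 90 kg | 10% | 11.1% |
| 91 kg | 9.9% | 9.9% |
| 95 kg | 5.3% | 5.3% |
| 100 kg or more | 0% | 0% |

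The full 10% needs a C1D1 weight of at most 100/1.10 = 90.9 kg, and the full 15% at most 100/1.15 = 87.0 kg. A gain just under 10% changes nothing.

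**Benchmarks.**
- Overdose: 10% to 15% is below 20%.
- Variation the note already tolerates: a loss just under 10% leaves the dose uncorrected, almost 1/0.90 − 1 = 11.1% high per actual kg.
- Dose levels: planned steps are ratios of 3.0, 3.33, 3.0, 2.0 and 2.0, so no planned level is crossed. The only listed step within 15% is 9 to 10 µg/kg (10/9 = 1.111), both potential intermediate levels. All other listed steps are at least 1.20.

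**Exposure inside the DLT window.** Doses after C1D1 that fall in the window:
- No step-dosing: Schedule A none; Schedule B one (C1D8).
- One, two or three steps (Table 10): Schedule A 2, 3, 4; Schedule B 3, 5, 7.

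One dose in each step-dosing count is C1D8, given at 0.5 × HTID. Raised by 10% to 15% it becomes 0.5 × 1.10 = 0.55 to 0.5 × 1.15 = 0.575 × HTID, still well under a dose already tolerated as an initial dose. Leaving it out, the counts are 1, 2, 3 on Schedule A and 2, 4, 6 on Schedule B.

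**The case against.** The strongest objection is that the governing text may lie elsewhere. Table 7 sends sites to the Pharmacy Instructions for dosing, and the choice of dosing weight is a natural subject for them. Table 11 also has a row for exactly this situation, and it says no change. Its Grade 2 or lower column is empty in almost every row, so the blank may mean little.

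There are safeguards too. Dose delay is named for peripheral edema. Section 6.2.2.1 allows delays, reductions and other adjustments, and Section 8 sends immediate safety concerns to the sponsor. Grade 3 or higher hypotension, dyspnea or oliguria accompanying a leak resumes one level lower; between planned levels that is a 2- to 3.3-fold cut, far larger than the rise at issue. Table 5 bases the capillary leak risk on high-dose IL-2 experience, not on reported NL-201 events.

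Much of this stands, and it limits the size of the point. It does not remove it. An unseen document cannot be assumed to hold an exception. The Table 11 row either conflicts with the note or leaves it in force. The milder safeguards are discretionary, while the note is mandatory, and the level reductions need a separate Grade 3 or higher event.

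A reader might infer that patients with capillary leak will be overdosed, or that escalation will assign the wrong dose level. The documents support neither. A 10% to 15% rise is below the overdose threshold, and levels are defined per kg, so the assigned level is unchanged.

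**Conclusion.** The point holds as a modest safety inconsistency. A binding rule, followed literally, can raise the µg dose by 10% or slightly more because of a sign of a suspected toxicity, and the protocol does not say how the rule relates to Table 11.

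This rests on three assumptions: that the adjustment is proportional to current weight, that the patient is considered fit to dose, and that the Pharmacy Instructions hold no contrary rule. The documents do not say how often a fluid gain of 10% or more would occur at Grade 2 or lower, so no expected number of affected doses can be given. Without step-dosing, the only exposed dose in the DLT window is C1D8 on Schedule B, which needs a gain of that size within about a week. Confidence is medium. It is worth correcting as a cheap improvement.

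**What to change.** Add to the weight note in Tables 1 to 4:

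*Weight gain attributed by the investigator to edema or fluid retention does not trigger an upward dose recalculation; keep the weight used for the most recent NL-201 dose calculated before the fluid retention (see Table 11).*

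This names a single dosing weight and leaves the 10% rule in place for every other weight change. At 70 kg and 3 µg/kg the dose stays at 210 µg. If the Pharmacy Instructions already contain such a rule, add a cross-reference to it in the note.

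The cost is one sentence in four tables. No new assessment is needed: weight is already taken at the dosing visits, and Section 6.2.2.1 already has the reason for any NL-201 dose change recorded on the CRF. The downside is that the investigator must judge whether the gain is fluid. A real gain in body mass misread as edema would leave the patient on a slightly low dose per kg.
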